6.1.2. Baseline Definition

The baseline for variables collected as part of the old diary (including the SF and rectal bleeding (RB) components of the Modified Mayo) will be calculated from valid entries obtained prior to baseline endoscopy preparation (see Appendix 1). The baseline endoscopy component of the Mayo will use the endoscopic appearance of the mucosa at the screening endoscopy. For other efficacy, health outcome, and safety assessments, baseline is defined as the last non-missing assessment recorded on or prior to the date of the first study drug administration at Visit 2 (Week 0).

Baseline for safety analysis is described in the safety section.

Change from baseline will be calculated as the visit value of interest minus the baseline value. If a baseline value or the value at the visit is missing for a particular variable, then the change from baseline is defined as missing.

6.1.3. Analysis Methods

For assessments of the binary efficacy endpoints and binary health outcomes, proportions for each weight class/treatment group along with the 95% confidence intervals (CIs) using the Wilson Score method (Wilson 1927; Newcombe 1998) will be provided. Non-responder imputation method will be used to estimate the percentage of patients achieving response across post-baseline visits.

Assessments of the continuous endpoints, descriptive statistics (n, mean, standard deviation [SD], minimum, first quartile, median, third quartile, and maximum) will be provided for each specified visit. Where appropriate, the mean and mean change from baseline with corresponding 95% CIs will be presented at each specified visit.

6.2. Adjustments for Covariates

This study is a multicenter, open-label PK study designed to evaluate the safety, PK, PD, and clinical response of mirikizumab in pediatric patients, and to provide data for dose confirmation for Phase 3. All patients will receive mirikizumab based on their baseline weight class for the Induction Period and Week 12 weight class for the Maintenance Period. Treatment comparisons are not planned to be performed, hence no adjustments for covariates will be warranted.

6.3. Handling of Dropouts or Missing Data

Intercurrent events (FDA 2021) are events which occur after the treatment initiation and make it impossible to measure a variable or influence how it should be interpreted. Examples of such

events include treatment discontinuation due to death or adverse events (AEs), rescue treatment, and loss to follow-up. The missing data methods described below handle intercurrent events in different ways and thus are relevant to different estimands.

The Schedule of Activities outlined in the protocol specifies the allowable windows for assessments. Assessments performed outside these windows will not be excluded from any analysis, but will be reported as a protocol deviation (see Section 6.15). While every effort will be made to reduce missing data, the missing data imputation method of NRI will be used when patients are permanently discontinued from study drug or otherwise have missing data. For the "as observed" analysis, only data from completers at the visit are relevant, and therefore the analysis does not need to deal with missing data.

For any interim analyses that occur, patients who, based on their treatment start date, would not have completed the visit corresponding to the selected endpoint at the time of the database lock will not be included in the analysis of that endpoint unless otherwise specified. Patients who have discontinued or otherwise have missing data and would have otherwise completed that visit at the time of database lock will be counted as non-responders for the interim analysis. For example, if a patient who discontinued at Week 12 of the study would have been in Week 24 of the study at the time of database lock, would not be included in the analysis of endpoints at Week 36 or Week 52. If that same patient who discontinued would have been at Week 48 at the time of the interim database lock if they had remained in the study, they would be counted as a non responder for Week 36, but not included in the Week 52 analysis.

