5.1. Overall Design

Study AMBU is a multicenter, open-label PK study designed to evaluate the safety, PK, pharmacodynamics (PD), and clinical response of mirikizumab in pediatric patients, and to provide data for dose confirmation for Phase 3.

The study population includes patients with moderately to severely active UC who have an inadequate response to, loss of response to, or are intolerant to non-biologic therapy for UC (biologic-naive), and/or those who have been exposed to at least 1 biologic and/or JAK inhibitor therapy for UC (biologic/JAK inhibitor-experienced).

Patients weighing >40 kg will receive a mirikizumab induction dose of 300 mg via IV infusion and patients weighing ≤40 kg will receive induction doses of 5 or 10 mg/kg via IV infusion at Weeks 0, 4, and 8. Enrollment will begin with the 300 mg and 5 mg/kg dose cohorts. Patients in the 10 mg/kg cohort will be enrolled after 5 patients in the 5 mg/kg dose cohort have received 4 weeks of mirikizumab, an evaluation of the available PK in the 5 mg/kg cohort (as described in Section 10.3.8.1) has been conducted, and enrollment of the 5 mg/kg dose cohort has been filled.

Patients who achieve a Modified Mayo Score (MMS) clinical response (see Table AMBU.5) at Week 12 will proceed to the maintenance period and receive SC doses of 200 mg (weight >40 kg), or 100 mg (weight >20 kg to ≤40 kg), or 50 mg (weight ≤20 kg) mirikizumab Q4W through Week 48.

Patients who do not meet the MMS clinical response definition at Week 12 may receive extended IV induction dosing (either at the same dose or for the 5 mg/kg dose cohort, escalate to the 10 mg/kg dose) for 12 more weeks or discontinue. Following the completion of IV dosing at Week 24, if the investigator determines that the patient has improved, the patient will proceed to the maintenance period and receive Q4W SC doses based on weight class through Week 48. If the investigator determines that sufficient improvement was not made, the patient will discontinue study drug and undergo procedures for early termination of the study drug, including post-treatment follow-up as described in the Schedule of Activities (Section 2).

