7.7. Concomitant Therapy

The list of prohibited medications and the list of permitted medications with dose stabilization guidance are provided in [Appendix 5](#) and [Appendix 6](#), respectively.

All concomitant medications (including medications for bowel preparations) taken during the study must be recorded in the Concomitant Medication eCRF. This includes concomitant medications for UC as well as for underlying conditions or diseases, and for AEs. All patients are encouraged to maintain their usual medication regimens for concomitant conditions or diseases throughout the study, unless those medications are specifically excluded ([Appendix 5](#)).

Stable doses of permitted UC concomitant medications (other than oral corticosteroids) are encouraged, unless dose modification is required due to AEs, or dose modification is otherwise specified in [Appendix 6](#). Patients taking oral corticosteroids are to follow the corticosteroid taper instructions described in Section [7.7.1](#).

Administration of prohibited UC medications for the management of symptoms of UC, approved or investigational, constitutes treatment failure. Use of such medications should not be withheld if, in the opinion of the investigator, failure to prescribe them would compromise patient safety. Patients who require a prohibited medication to treat their UC (see [Appendix 5](#)) need to be discontinued from study drug and complete an early termination visit (ETV) and post-treatment follow-up visits.

If a concomitant medication is needed to treat an AE or for appropriate medical management, the investigator should base decisions on patient and clinical factors. Local administration of corticosteroids (for example, intranasal, inhaled, intraarticular) are allowed as required for the management of pre-existing conditions and AEs. A patient who initiates a prohibited medication for a non-UC indication should be discussed with the medical monitor.

Patients are allowed to continue or initiate any concomitant medication for non-UC conditions, diseases, or AEs, insofar that the medication is not specifically prohibited ([Appendix 5](#)) and use of the medication complies with the dosing requirements as described in [Appendix 6](#).

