6.3.1. Non-Responder Imputation (NRI)

For analysis of categorical efficacy and health outcomes variables, missing data will be imputed using an NRI method. Patients will be considered non-responders for the NRI analysis if they do not meet the categorical efficacy criteria or have missing clinical efficacy data at a time point of interest.

The NRI method may be used when the estimand of interest uses the composite strategy (FDA 2021) for handling intercurrent events. In this strategy, patients with any intercurrent events that lead to the permanent discontinuation of assigned study treatment are defined to have failed treatment for all subsequent time points.

In addition, patients who were not adequately assessed to determine if they meet the clinical requirements for response at the time point of interest are also considered to have failed treatment.

For any interim analyses that occur, patients who, based on their treatment start date, would not have completed the visit corresponding to the selected endpoint at the time of the database lock will not be included in the analysis of that endpoint. Patients who have discontinued or otherwise have missing data and would have otherwise completed that visit at the time of database lock will be counted as non-responders for the interim analysis.

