	Each subscore is on a 4-point scale, ranging from 0 to 3.	PGA subscore	Possible values are: (0) Normal (1) Mild disease	Single item. Missing if missing.

Measure	Description	Variable	Derivation / Comment	Definition of Missing
			(2) Moderate disease	
			(3) Severe disease	
		Modified Mayo Score	Calculated as: SF + RB + ES.	Missing if SF, RB or ES
		(MMS)		subscores are missing.
		Partial Mayo Score	Calculated as: SF + RB + PGA.	Missing if SF, RB or PGA subscores are missing.
		Alternate MMS Clinical Remission	SF subscore = 0, or SF = 1 with a ≥1-point decrease from baseline, and RB subscore = 0, and ES subscore = 0 or 1 (excluding friability)	Missing if SF, RB, or ES subscores are missing.
		MMS Clinical	SF subscore = 0 or 1	Missing if SF, RB, or ES
		Remission	RB subscore $= 0$, and	subscores are missing.
			ES subscore = 0 or 1 (excluding friability)	J
		MMS Clinical Response	A decrease in the MMS of ≥2 points and ≥30% decrease from baseline, and A decrease of ≥1 point in the RB subscore from baseline or a RB score of 0 or 1	Missing if baseline or Week 12 MMS is missing.
		Endoscopic Remission	ES = 0 or 1 (excluding friability).	Missing if ES is missing.
		Symptomatic Remission	$SF = 0$, or $SF = 1$ with a ≥ 1 -point decrease from baseline and $RB = 0$	Missing if SF or RB is missing.
		Time to first symptomatic remission	For patients who are observed to meet the remission criteria during the Induction Period, time will be from the start of the Induction Period to the first measurement date where the patient met the remission criteria based on weekly averages.	Patients not observed to meet remission criteria during the Induction Period will be censored after the date of their last measurement during the Induction Period.

Measure	Description	Variable	Derivation / Comment	Definition of Missing
			CCI	
		Time to first symptomatic response	For patients who are observed to meet the response criteria during the Induction Period, time will be from the start of the Induction Period to the first measurement date where the patient met the response criteria based on weekly averages.	Patients not observed to meet response criteria during the Induction Period will be censored after the date of their last measurement during the Induction Period.
		Endoscopic subscore of 0	ES = 0.	Missing if ES is missing.
		Total Symptomatic Score	Calculated as SF + RB.	Missing if SF or RB is missing.

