		Endoscopic Response	A decrease in the ES of ≥1 point compared to baseline.	Missing if ES is missing.
		SF component of clinical remission	SF = 0, or $SF = 1$	Missing if SF is missing.
		RB component of clinical remission	RB = 0	Missing if RB is missing.
		Corticosteroid-free remission at Week 52	Corticosteroid-free remission without surgery at Week 52, defined as: Clinical remission at Week 52, and No corticosteroid use or UC-related surgery for ≥12 weeks prior to Week 52	NRI if any component is missing.
		Loss of Clinical Response	CCI	

Measure	Description	Variable	Derivation / Comment	Definition of Missing
Urgency NRS	CCI	Urgency NRS Score	Calculated by averaging data from all available diary entries of Urgency NRS for a 7 day period as described in Appendix 1.	Missing if fewer than 4 available measurements in the relevant 7 days (see Appendix 1).
Abdominal Pain NRS	The Abdominal Pain NRS is a single patient-reported item that measures the "worst abdominal pain in the past 24 hours" using a 6-point scale ranging from 0 (no pain) to 5 (worst possible pain) for 8-11 years old, and 11-point NRS ranging from 0 (no pain) to 10 (worst possible pain) for children < 8 years old as completed by a caregiver and those 12-17 years old.	Abdominal Pain NRS Score	Calculated by averaging data from all available diary entries of Abdominal Pain NRS for a 7 day period as described in Appendix 1.	Missing if fewer than 4 available measurements in the relevant 7 days.
PGIC	The Patient's Global Impression of Change (PGIC) scale is a patient-rated instrument designed to assess a patients' rating of change in their symptom(s). Responses are graded on a 7-point Likert scale. Patients or caregivers will record their response on the PGIC electronically as source data in the tablet device at appropriate visits.	PGIC Score	Single Item	Single item, missing if missing. No imputation.
PGRS	Patient's Global Rating of Severity (PGRS) is a 1-item patient-rated questionnaire designed to assess the patients' rating of their disease symptom severity over the past	PGRS Score	Calculated by averaging data from all available diary entries of PGRS for a 7 day period as described in Appendix 1.	Missing if fewer than 4 available measurements in the relevant 7 days.

Measure	Description	Variable	Derivation / Comment	Definition of Missing

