	medical history and adverse event eCRFs. Extraintestinal manifestations include, but are not limited to: uveitis, peripheral arthritis, ankylosing spondylitis, aphthous stomatitis, arthralgia, autoimmune hepatitis, cholelithiasis, deep vein thrombosis, iritis, nephrolithiasis, erythema nodosum, osteopenia, osteoporosis, pancreatitis, sclerosing cholangitis, pyoderma gangrenosum, sacrolitis and skin vasculitis NOS.	Resolution of Baseline EIMs	Complete resolution of baseline EIMs at Week 12 or 52. If a patient has multiple baseline EIMs, then at least one of the EIMs must have resolved.	No Imputation

Abbreviations: CFB = change from baseline; NOS = not otherwise specified; NRI = non-responder imputation; NRS = Numeric Rating Scale; PUCAI = Pediatric Ulcerative Colitis Activity Index; Q12W = every 12 weeks.

 Table AMBU.6.5.
 Description of Secondary Efficacy/Health Outcomes Analyses

		Analysis Method	Population	
Measure	Variable	(Section 6.1.3)	(Section 6.1.1)	Time Point(s)
Mayo Score and components	MMS Clinical Remission	Proportion for each weight/treatment dose group along with the 95% 2-sided CI with NRI and as observed	mITT	Weeks 12 and 52
			mITT who are remitters from	Week 52
			Week 12	
			mITT who are MMS clinical	Week 52
			responders from Week 12	
	MMS Clinical Response	Proportion for each weight/treatment	mITT	Weeks 12 and 52
		dose group along with the 95%	mITT who achieve MMS	Week 52
		2-sided CI with NRI and as observed.	clinical response at Week 12	
	Corticosteroid-free	Proportion for each weight/treatment	mITT	Week 52
	remission	dose group along with the 95%		
		2-sided CI with NRI and as observed.		
	Endoscopic Remission	Proportion for each weight/treatment	mITT;	Weeks 12 and 52
		dose group along with the 95%	mITT who are in endoscopic	Week 52
		2-sided CI with NRI and as observed.	remission at Week 12	
	Endoscopic subscore of 0	Proportion for each weight/treatment	mITT	Weeks 12 and 52
		dose group along with the 95%		
		2-sided CI with NRI and as observed.		
	Symptomatic remission	Proportion for each weight/treatment	mITT	At all scheduled visits
		dose group along with the 95%		
		2-sided CI with NRI and as observed.		
PUCAI	PUCAI clinical remission	Proportion for each weight/treatment	mITT	Weeks 12 and 52
		dose group along with the 95%	mITT who achieve PUCAI	Week 52
		2-sided CI with NRI and as observed.	clinical remission at Week 12	
			mITT who achieve PUCAI	Week 52
			clinical response at Week 12	

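### Composite endpoints already failed on an observed component are coded as missing and leave the as-observed denominator, and corticosteroid-free remission follows a different rule

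*SAP*

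**What the plan says.** SAP Section 6.1.3 names the main method for binary endpoints: "Non-responder imputation method will be used to estimate the percentage of patients achieving response across post-baseline visits". For most binary secondary endpoints, Table AMBU.6.5 then asks for two results: "Proportion for each weight/treatment dose group along with the 95% 2-sided CI with NRI and as observed". Table AMBU.6.6 asks for the same pair for alternate MMS remission. Section 6.3 describes the second result by saying that "only data from completers at the visit are relevant, and therefore the analysis does not need to deal with missing data".

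Whether a child has an outcome at a visit is settled in Table AMBU.6.4. MMS remission needs the stool frequency (SF), rectal bleeding (RB) and endoscopic (ES) subscores all to pass, and its missing-data cell reads "Missing if SF, RB, or ES subscores are missing". Alternate MMS remission has the same cell. Symptomatic remission is missing if SF or RB is missing. The two histologic-endoscopic endpoints are missing if any part of their definition is missing.

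Corticosteroid-free remission at Week 52 differs. Its cell reads "NRI if any component is missing", while Table AMBU.6.5 still asks for it both with NRI and as observed.

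**The concern.** Each of these composites requires every component to pass, so one observed failing component settles the result. Coding the child as missing discards an outcome that is in effect known, and it does so only for failures: a success needs every component observed, so no success can be lost this way. The as-observed rate and its 95% interval therefore lean in the favourable direction for reasons of coding alone.

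The corticosteroid-free remission cell leans the other way. A child assessed at Week 52 whose observed components leave the outcome open is left out of as-observed MMS remission, but counts as a failure in as-observed corticosteroid-free remission. The same column heading would then cover two conventions.

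At stake is the reading of the as-observed column beside NRI in groups of about 10 children, where one or two children move a rate visibly.

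**Working it through.** The plan gives no expected rate, dropout or missing-data figure for these endpoints, so there is nothing of its own to reproduce. All patient counts below are assumptions. The group size of 10 is the SAP Section 5.2 target for the >40 kg category. The ≤40 kg category has about 20 children over two induction doses, and the split is not stated.

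**Step 1: which incomplete cases are already decided?** For MMS remission (SF 0 or 1, RB 0, ES 0 or 1):

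| Observed | Missing | Can the child be in remission? | Code in Table AMBU.6.4 |
|---|---|---|---|
| ES = 3 | SF and RB (fewer than 3 valid diary days) | No | Missing |
| RB = 2 | ES (no endoscopy) | No | Missing |
| SF = 0, RB = 0 | ES | Undecided | Missing |

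Only the third row is truly missing. The same logic applies to the histologic-endoscopic endpoints, where an ES of 2 or 3 fails endoscopic remission whatever the biopsy shows. It also applies to symptomatic remission, although SF and RB come from the same diary and will less often be missing separately.

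**Step 2: effect on the rate.** Let N be the children in the group, x the successes, m the determined failures coded as missing, and u the other children without an outcome.

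- NRI: x/N. All m and u children count as failures under either coding, so this does not change.
- As observed, current coding: x/(N − m − u).
- As observed, determined failures kept: x/(N − u).

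The ratio of current to corrected is (N − u)/(N − m − u), which is never below 1.

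**Step 3: numbers.** Take N = 10, x = 3, u = 0. The 95% Wilson interval has centre (p + z²/2n)/(1 + z²/n) and half-width z√(p(1 − p)/n + z²/4n²)/(1 + z²/n), with z = 1.96.

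| m | As observed, current coding | As observed, corrected |
|---|---|---|
| 0 | 3/10 = 30.0% (10.8–60.3) | 30.0% |
| 1 | 3/9 = 33.3% (12.1–64.6) | 30.0% |
| 2 | 3/8 = 37.5% (13.7–69.4) | 30.0% |
| 3 | 3/7 = 42.9% (15.8–75.0) | 30.0% |

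With 5 successes of 10, the same losses give 5/9 = 55.6%, 5/8 = 62.5% and 5/7 = 71.4% instead of 50.0%. Over these cases the excess runs from 3.3 to 21.4 points. The intervals are wide and overlap heavily.

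**Step 4: corticosteroid-free remission.** Take 10 children assessed at Week 52: 3 in remission and free of corticosteroids and surgery, 5 fully observed and not in remission, and 2 with passing diary scores, no corticosteroids or surgery, and no endoscopy. As-observed MMS remission drops the last 2: 3/8 = 37.5%. As-observed corticosteroid-free remission, read literally, counts them as failures: 3/10 = 30.0%. The 7.5-point difference comes from coding alone.

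**The case against.** The strongest reply is that Section 6.3 openly defines a summary of completers, shown beside NRI, which is the named method and addresses all treated children. No treatment comparison is planned and the primary endpoint is pharmacokinetic. That stands. A completer rate is a legitimate description if labelled as one.

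A reader might infer more: that the as-observed rates are biased for most endpoints because children who do badly are removed. The protocol does say of children finishing extended induction that "If the investigator determines that sufficient improvement was not made, the patient will discontinue study drug", and also that "Administration of prohibited UC medications for the management of symptoms of UC, approved or investigational, constitutes treatment failure". Under NRI, children who stop permanently "are defined to have failed treatment for all subsequent time points". But the Week 24 rule applies only to Week 12 non-responders given extended induction. It cannot affect any Week 12 endpoint, or Week 52 outcomes among Week 12 MMS responders. Other routes to stopping exist, and the documents do not say how many children would take them. This supports a clear label, and no finding of bias across endpoints.

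A reader might also infer that as-observed corticosteroid-free remission simply repeats NRI. That is not shown. Section 6.3 still limits as-observed to completers, so discontinued children leave its denominator; the two results coincide only if those children are treated as having missing components. The cell may have been meant for the NRI run alone, but the SAP does not say so.

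Nor is it right that the pair cannot show dependence on missing data. For most endpoints the two rates share a numerator and differ by the children left out, which is informative.

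**Conclusion.** Two small specification faults hold. First, composites already failed on an observed component are coded as missing, so the as-observed rate can only be pushed up: from 30% to between 33% and 43% with 1 to 3 such children in a group of 10. Those counts are assumed, and the documents do not say how many children would be partly assessed. Single-item endpoints, such as endoscopic remission and ES = 0, are not exposed. Second, corticosteroid-free remission carries an imputation rule inside its definition that conflicts with its requested as-observed analysis. The size again depends on the number of partly assessed completers.

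Neither fault touches the NRI results or the primary objective. This is a worthwhile tidying of the SAP and no threat to the trial's conclusions.

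**What to change.** 1. In Table AMBU.6.4, code MMS and alternate MMS remission, symptomatic remission, and histologic-endoscopic improvement and remission as not achieved when any observed component fails. Code them as missing only when the observed components leave the outcome undecided.
2. Give corticosteroid-free remission the same rule, and apply NRI only in the NRI analysis. In the Step 4 example the two undecided children then leave both as-observed denominators, and both rates are 3/8.
3. In Section 6.3, replace the statement that missing data need no handling. Say that the as-observed summary describes only patients assessed at the visit, a group selected partly by discontinuation for poor outcome, and show n/N beside each rate.
4. Do not count discontinued patients as non-responders within the as-observed summary. That would bring in the kind of imputation that item 2 removes and blur the contrast with NRI.

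The cost is a few lines of SAP text, minor programming and slightly less favourable as-observed rates for the composites. No new data are needed and trial conduct does not change.
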